TITLE

A randomized trial of vaginal prep solutions to reduce bacteria colony counts in patients having a vaginal surgery.

INVESTIGATORS

[name], [name], [name]

SUMMARY OR ABSTRACT

This is a randomized trial comparing the effectiveness of 4 vaginal prep solutions (betadine, baby shampoo, TechniCare and Peridex) on reducing bacterial colony counts during surgery preparation. Women undergoing a vaginal surgery will be enrolled into the trial prior to surgery. Target sample size per group is 15 patients. During standard surgical prep, a vaginal swab will be taken to assess the initial colony counts for aerobic and anaerobic bacteria. After the initial swab, the vagina will be prepared using one of the prep 4 solutions (betadine, baby shampoo, TechniCare or Peridex). After a predefined 10 minutes, the area will be re-swabbed to determine pre-procedure colony counts. A third swab will be taken following completion of the procedure to determine post-procedure colony counts. Laboratory analyses for raw colony counts, sensitivities, identification (using MALDI-TOF) will be performed. We expect that there will be reduced colony counts at the pre-procedure point with baby shampoo having the least reduction, followed by betadine and TechniCare, then Peridex. Patient reported outcomes for vaginal itching and burning as well as patient report of any treatment for vaginal infection will be collected by telephone at 2 days, 2 weeks and 1 month post-surgery.

BACKGROUND AND LITERATURE REVIEW

Antiseptic preparation for surgical incision sites has greatly reduced postoperative infections. However, surgical site infections (SSI) are still the leading cause of hospitalizations after

surgery. With the application of antiseptic preparation, a reduction in bacterial counts follows.

The rate at which the bacterial counts rise between preparation and incision may be of variation depending on the surgical antiseptic scrub.

Betadine (Povidone- iodine), Peridex (Chlorhexidine), baby shampoo and TechniCare (chloroxyne) are all surgical scrubs approved for the preparation of vaginal access surgeries.

While there has been controversy on the use of Chlorohexidine for vaginal preparation surgery, due to its labeling as a cause for irritation, studies have shown that when 2-4% Chlorhexidine is used in the vaginal area there are little to no signs of irritation and the bacteria counts post incision are less than the bacterial counts for povidone iodine^{1,2}. Baby shampoo can also be used as an effective antiseptic scrub with no irritation and no statistical difference in bacterial count reduction as compared to povidone-iodine³. Little research has been done to look at the antiseptic power of Chloroxylenol in vaginal surgeries. However, when used as a root canal antiseptic it can reduce bacteria counts by 99.9%⁴. This is illustrative of its capability to reduce bacteria on a mucus membrane similar to the vagina.

There is literature that shows the antiseptic power of Betadine, Peridex, Baby shampoo and TechniCare for post-incisional bacteria counts, but little is known about the pre-incisional power of these scrubs for vaginal access surgeries.

SPECIFIC AIMS OR OBJECTIVES

The aim of this study is to understand the power of vaginal surgical scrubs before and after procedure completion. This will be done by collecting bacterial samples before antiseptic preparation, 10 minutes after antiseptic preparation, and after completion of the procedure along with follow-up data of irritation, infection post-surgery, and infection risk factors of each patient.

SIGNIFICANCE TO PATIENT, INSTITUTION, PROFESSION, OR ALL

Vaginal preparation research provides beneficial knowledge to hospitals and physicians in the prevention of surgical site infections (SSI). This specific project will provide insight regarding the bacteria-eliminating power of four different surgical scrubs used on the vaginal mucous membrane. There is potential for this study to determine the most effective scrub for vaginal surgeries, as well as correlate pre-procedure bacterial counts and likelihood of surgical site infections. The information collected from this study could benefit future patients and hospitals alike in terms of reducing the risk of SSI's. The risks of this study could be unidentified allergies to any of the surgical scrubs, or a loss of patient data. These are unlikely risks due to the protocol of the study.

METHODS

This study will use block randomization. There will be four arms of the study one for each of the four surgical scrubs. There will be approximately 15 patients per arm. Patients undergoing surgeries which require a vaginal antiseptic preparation will be recruited from Wright State Physicians Obstetrics and Gynecology as well as other participating groups at Miami Valley Hospital. Procedures included in the study are procedures in which a vaginal preparation is performed, including procedures with a vaginal incision (hysterectomy, incontinence procedures), as well as general laparoscopic procedures (diagnostic laparoscopy, salpingectomy, oophorectomy, etc). Procedures excluded from the study are procedures which involve: any local infectious process such as cellulitis or abscess, have significant risk of washout of the vaginal preparation (hysteroscopy or vaginoscopy), any procedures for invasive cancer diagnoses, or procedures with significant risk of bleeding such as dilation and curettage (both for sampling or pregnancy-related), or endometrial ablation. Revision surgeries will also be excluded to decrease any complications. Patients who consent to the study will be given a ID and

will be randomly assigned to one of the four arms. Patients will be excluded if an allergy to any of the scrubs is listed or found. Each recruited patient will be over the age of 18 with ability to consent on their own.

Each patient will be given a standard prophylaxis 30 minutes before surgery. After prophylaxis administration and before surgical antiseptic preparation, a 10 second swab will be taken of the vagina making sure to span the surface area of the vaginal canal with avoidance of the cervix. The swab will then be broken off into a tube labeled with the patient ID, date, and “pre-scrub.” The patient will then undergo antiseptic preparation with the assigned surgical prep. A standard procedure of application will be done for each of the arms. Ten minutes after application, another swab will be taken using the same procedure as the “pre-scrub” swab. This swab will be broken off in a tube labeled with the patient ID, date, and “post-scrub.”¹ Following the conclusion of the procedure, a third swab will be taken using the same procedure as the two pre-incision swabs. The third swab will then be broken off into a tube labeled with the patient ID, date, and “post-procedure-swab.” The swabs will then be transported to CompuNet where they will be analyzed for aerobic, anaerobic bacteria and fungal colonies using Matrix Assisted Depolarization/Ionization Time of Flight mass spectrometry (MALDI-TOF).

The data of colony counts will be collected from CompuNet. BMI, age, prophylaxis, postmenopausal information, diabetic information, smoking history, surgical duration, complication in surgery, and length of hospital stay will all be collected from patient records. No patient identifiers will be collected⁵. Patients will be followed up on their surgery approximately two days, two weeks and a month after surgery to get information on irritation and/or surgical infection. This data will be collected either be phone call or at post-surgical follow-up appointment at Wright State Physicians. The South Hampton Grading Scheme for Surgical

Wounds will be used to Quantify Each patients level of irritation and/or infection. The scale is a Zero to Five score, with Zero being no irritation or infection and Five being severe irritation or infection¹⁵.

One potential obstacle of this study could be recruitment of patients. Patients will not be given incentive for participation and will not acquire any direct benefit from the study. Another potential issue may arise from the size of the study; there may not be enough subjects recruited for each arm of the study to find a detectable and significant difference in the use of one surgical scrub over another. There may also not be sufficient power to detect a difference in the risk of post-operative surgical site infections.

Precautions will need to be taken for allergies. A recruited patient may not be aware of personal allergies to the surgical scrubs. This would put the patient in harm if they are assigned to a scrub that they are allergic to. Since data will be collected from the patient's medical records, precautions will be taken to avoid loss of patient identifiers. All research investigators will only utilize the patients assigned research ID. This will both protect the patient and avoid bias.

Statistical Analysis Plan

Bacterial and fungal colony counts will be coded as positive if counts are ≥ 5000 colonies/mL

and negative if < 5000 colonies. Statistical analyses will be conducted as follows:

Baseline characteristics will be compared with Chi square (categorical data) and ANOVA (continuous data) to determine potential differences for demographic and clinical characteristics and for colony counts (positive vs negative) at the pre-scrub sample collection.

Each of the 3 target scrubs (baby shampoo, chlorhexidine and chloroxyne) will be compared to povidone-iodine as the standard of care using Fisher's Exact tests for each pair comparison at the

post-scrub and post-procedure collections.

REFERENCES

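### At the post-procedure swab, vaginal-incision and laparoscopic cases are pooled, planned procedure type is not listed for collection, and only unadjusted Fisher tests are planned: the test is valid, but a chance imbalance would go unseen and power is lost to conservatism

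*Combined protocol and SAP*

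**What the plan says.** The aim covers both sides of the operation: "The aim of this study is to understand the power of vaginal surgical scrubs before and after procedure completion" (Specific Aims or Objectives). The Methods section enrols procedures "including procedures with a vaginal incision (hysterectomy, incontinence procedures), as well as general laparoscopic procedures (diagnostic laparoscopy, salpingectomy, oophorectomy, etc"), and excludes those that "have significant risk of washout of the vaginal preparation (hysteroscopy or vaginoscopy"). Allocation is described in one sentence, "This study will use block randomization", with no stratum and about 15 patients per arm.

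The timing of the swab is given as "Following the conclusion of the procedure, a third swab will be taken", so the operation lies between the prep and this measurement. The items taken from records are: "BMI, age, prophylaxis, postmenopausal information, diabetic information, smoking history, surgical duration, complication in surgery, and length of hospital stay will all be collected". Planned procedure type is not among them.

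The Statistical Analysis Plan compares the arms at baseline "to determine potential differences for demographic and clinical characteristics", without listing which. Each of the three other scrubs "will be compared to povidone-iodine as the standard of care using Fisher's Exact tests for each pair comparison", at the post-scrub and post-procedure collections. No stratified test, adjusted model or risk-difference estimate is planned, and no significance level is stated.

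**The concern.** One group of patients has a vaginal incision between the second and third swabs and the other does not. The washout exclusion shows that the protocol accepts that a procedure can disturb the prep. If procedure type affects positivity at the third swab, a chance imbalance between two arms of 15 would move the observed difference, and as planned neither the baseline table nor the test would necessarily reveal it.

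A second point concerns the test itself. The Methods section concedes that the trial may be too small to find a difference. Fisher's test at 15 per arm runs far below a 5% level and so gives up power that another exact test would keep.

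**Working it through.** The plan gives no rates, effect size, significance level or power behind 15 per arm, so there is no figure to reproduce. From the plan: 15 per arm, three comparisons with povidone-iodine, a positive/negative outcome, no strata. Assumed: two-sided 0.05, all positive rates, the share with a vaginal incision, and the gap in positive rate between procedure types.

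**1. Chance of imbalance.** Let X be the number of vaginal-incision patients in an arm, Binomial(15, share), independent between arms. For one pair, sum P(a)P(b) over |a − b| ≥ 4. For any of the three pairs sharing the povidone-iodine arm, take 1 − Σ P(c)·[P(|X − c| ≤ 3)]³.

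| Assumed share | One pair | Any of three |
|---|---|---|
| 50% | 20% | 43% |
| 30% | 16% | 36% |
| 20% | 11% | 25% |
| 10% | 3% | 8% |

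**2. Size of the shift.** Shift = gap × 4/15. Gaps of 10, 20, 30 and 40 points give 2.7, 5.3, 8.0 and 10.7 points. The standard deviation of the risk difference at 65% vs 25% is √(0.65×0.35/15 + 0.25×0.75/15) = 0.166, about 17 points.

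**3. Overall validity.** With equal rates in both arms, exact enumeration of two Binomial(15, p) counts gives Fisher an error of about 1.1% to 1.8% over the settings examined. Its maximum over all p is 1.8%. Boschloo's test (Fisher's p-value as the statistic, with its tail probability maximised over the common rate) has a maximum of 4.3% at 15 vs 15 and keeps every Fisher rejection.

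**4. Error given an imbalance of 4 or more** (no scrub effect, 50% share; Fisher and Boschloo by enumeration, stratified mid-p from 200,000 simulated trials per setting):

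| Rates by type (gap) | Fisher | Boschloo | Stratified mid-p |
|---|---|---|---|
| 35/55% (20) | 2.1% | 5.2% | 5.0% |
| 30/60% (30) | 2.7% | 6.4% | 4.7% |
| 25/65% (40) | 3.5% | 8.0% | 4.5% |
| 20/80% (60) | 5.5% | 12.5% | 4.2% |

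**5. Power of the pooled tests** (exact). At 65% vs 25%, Fisher has 0.436 and Boschloo 0.591. At 30% vs 5%, they have 0.275 and 0.435. The gains are about 16 points in each case, and they come from replacing Fisher, not from procedure type.

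**6. What stratifying adds, like for like.** At 15 vs 15 the pooled mid-p test has the same rejections as Boschloo, so it is the fair comparator for stratified mid-p.

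| Average rates, gap, share | Pooled mid-p | Stratified mid-p |
|---|---|---|
| 65% vs 25%, gap 0, 50% | 0.59 | 0.59 |
| 65% vs 25%, gap 20, 50% | 0.59 | 0.61 |
| 65% vs 25%, gap 40, 50% | 0.59 | 0.68 |
| 25/35% vs 0/10%, gap 10, 50% | 0.44 | 0.38 |
| 25/35% vs 0/10%, gap 10, 20% | 0.49 | 0.42 |

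In the last two rows the figures before and after each slash are the rates in the two procedure types, and the share is that of the higher-rate type. Stratifying gains 2 points at a 20-point gap and 9 at a 40-point gap when rates are 65% vs 25%. It loses 6 to 7 points when rates are low and the gap is small. The standard deviation of the Mantel-Haenszel risk difference, relative to the crude one, is about 2% larger with no gap and 9% smaller at a 40-point gap.

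**The case against.** The strongest reply is that the planned test is not misled. Even given an imbalance of 4 or more, Fisher stays below 5% at gaps up to 40 points and passes it only at an assumed 60-point gap. That stands. A reader might infer a biased comparison or an inflated false-positive rate, but randomisation rules out the first on average and step 3 rules out the second.

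The premise is also inferred. A reader might take the washout exclusion as evidence that vaginal-incision and laparoscopic cases differ at the third swab. It shows only that some procedures were thought able to disturb the prep, and removing those procedures, together with those at risk of bleeding, narrows whatever difference remains. Nor does the point reach the 10-minute swab, which is taken before incision and is the subject of the hypothesis in the Summary.

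The unlisted clinical characteristics in the baseline comparison, or the infection risk factors mentioned in the aims, could include procedure type, and it could be retrieved from records later. That softens the point but does not close it, because neither place names procedure type and a factor chosen after results are seen carries less weight.

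Finally, it is tempting to make the stratified test the main test. The low-rate rows in step 6 do not support that: stratified mid-p still beats planned Fisher in the settings examined, but it can lose to a pooled test of the same kind. An unadjusted test at 15 per arm is a defensible choice.

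**Conclusion.** The point holds as one to consider, with medium confidence. As planned, the trial would not necessarily show how procedure type fell between arms, although the chance of a difference of 4 or more in one pair is 20% at a 50% share and 3% at a 10% share. The resulting shift is about 3 to 11 points at gaps of 10 to 40 points, smaller than the standard deviation of about 17.

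The planned analysis is valid and unbiased. Its definite cost is conservatism: about 11 to 16 points of power in the settings examined. Protection against imbalance is a separate and conditional benefit that depends on a gap the documents neither state nor imply. Recording and displaying procedure type requires no assumed gap and is the most secure part of the recommendation.

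**What to change.** 1. Record planned procedure type (vaginal incision yes/no) before randomisation and show it by arm in the baseline table. If enrolment has begun, take it from pre-operative records (assumed available) without knowledge of arm or swab result.
2. At the post-procedure swab, replace pooled Fisher with pooled Boschloo. It loses no Fisher rejection and keeps the 5% level overall. It does not adjust for imbalance: its error can reach about 6% to 8% given an imbalance of 4 or more at gaps of 30 to 40 points.
3. For that reason, pre-specify one supportive analysis: an exact conditional test stratified by planned procedure type, with mid-p, plus the Mantel-Haenszel risk difference. Define mid-p in the SAP as the probability of all outcomes no more likely than the observed one, counting those tied with it at half. The doubled one-sided form loses 2 to 3 points of power.
4. Use this one two-level factor only. Surgical duration is known only after randomisation and should not be the adjustment factor.

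Cost: one data field, one table row and a short SAP edit, with no extra patients. State the downsides in the SAP: stratifying may gain little, or lose up to about 7 points of power when positive rates are low and the gap is small, and mid-p does not strictly guarantee the 5% level (simulated overall error 3.3% to 5.0%). The stratified test should therefore stay supportive.

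### With no pre-scrub symptom or treatment question, post-operative irritation reported by arm cannot be separated into new and pre-existing

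*Combined protocol and SAP*

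**What the plan says.** **When symptoms are asked.** The Summary collects "Patient reported outcomes for vaginal itching and burning as well as patient report of any treatment for vaginal infection", and these "will be collected by telephone at 2 days, 2 weeks and 1 month post-surgery". The Methods give the same three times for irritation: "Patients will be followed up on their surgery approximately two days, two weeks and a month after surgery to get information on irritation". Neither section gives a time point before surgery.

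**How they are graded.** The Methods apply a wound grading scheme: "The scale is a Zero to Five score, with Zero being no irritation or infection and Five being severe irritation or infection". This is an absolute score. No change from a starting value is defined.

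**What is recorded before the scrub.** The Methods describe a swab: "After prophylaxis administration and before surgical antiseptic preparation, a 10 second swab will be taken of the vagina". The items taken from patient records are "BMI, age, prophylaxis, postmenopausal information, diabetic information, smoking history, surgical duration, complication in surgery, and length of hospital stay". Vaginal symptoms and current treatment for vaginal infection are not among them.

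**Eligibility.** The Methods exclude procedures involving a local infectious process, with cellulitis and abscess as examples. Itching, burning and irritation are not named.

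**Aim and analysis.** The Specific Aims include "follow-up data of irritation, infection post-surgery, and infection risk factors of each patient". The SAP compares demographic and clinical characteristics and pre-scrub colony status at baseline, then tests colony status at the two later swabs. It contains no analysis of irritation.

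**The concern.** The protocol takes a baseline for bacteria but none for symptoms. The participants are gynaecological surgery patients, and the plan records postmenopausal and diabetic status. Some of them may already have itching or burning, or be under treatment for a vaginal infection, when they arrive for surgery. If such a woman gives the same answer at day 2, her report looks exactly like that of a woman whose symptoms began after the scrub.

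Two things are at stake. The irritation rate reported for each scrub will include symptoms that were there beforehand, and any true difference between scrubs will look smaller than it is. The Background presents irritation as the source of the controversy over chlorhexidine, so a by-arm irritation table will be read with interest. Once the scrub has been applied, the missing answer cannot be recovered by later analysis.

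**Working it through.** There is no planned figure to reproduce. The documents give no irritation rate, no prevalence of prior symptoms, and no alpha, power or effect size behind the 15 per arm. Everything below is therefore illustrative.

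**Inputs**
- From the Summary and Methods: n = 15 per arm, randomized.
- Assumed: b = share of women with prior symptoms that persist to follow-up, the same in every arm in expectation, at 10%, 20% or 30%.
- Assumed: new irritation, independent of prior symptoms, of r1 = 5% under one scrub and r2 = 40% under another.
- Assumed: two-sided Fisher's exact test at 0.05, computed by exact binomial enumeration. The SAP uses this test for colony status, not for irritation.

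**Step 1: what is observed without a baseline answer.** Observed rate = b + (1 − b)r. The observed difference is therefore (1 − b)(r2 − r1), so the true difference shrinks by exactly the share b.

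| b | Observed rates | Observed difference |
|---|---|---|
| 0% | 5% v 40% | 35 points |
| 10% | 14.5% v 46% | 0.9 × 35 = 31.5 points |
| 20% | 24% v 52% | 0.8 × 35 = 28 points |
| 30% | 33.5% v 58% | 0.7 × 35 = 24.5 points |

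The inflation is larger in relative terms where true irritation is low: at b = 20%, a scrub with 5% new irritation would be reported at 24%.

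**Step 2: power with and without the baseline answer.** With a baseline answer there are two simple options. One counts new symptoms over all 15 women, with rates (1 − b)r. The other restricts to women who were symptom-free beforehand, with rates r and the number of such women in each arm binomial(15, 1 − b).

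| b | No baseline question | New symptoms, all 15 | Symptom-free women only |
|---|---|---|---|
| 10% | 30.7% | 44.2% | 51.1% |
| 20% | 20.2% | 36.0% | 43.1% |
| 30% | 14.5% | 27.5% | 34.8% |

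If no woman had prior symptoms, power would be 51.9%. That is not the right comparator, because asking the question does not remove the prior symptoms. The gain from asking is the difference between columns in the table.

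**Step 3: a smaller true difference.** With new irritation of 5% v 20%, power is 8.3% when no one has prior symptoms. At b = 10% to 30% it lies between about 3% and 9% under all three approaches.

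**Step 4: false positives.** If both scrubs cause 5% new irritation, the observed rates are equal in expectation. The Fisher test then rejects in 1.2%, 1.8% and 1.6% of trials at b = 10%, 20% and 30%, well under 5%.

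**The case against.** A reader might infer that women with prior symptoms are counted as scrub reactions. The documents do not support this. They collect and grade symptoms but contain no rule attributing a symptom to the scrub. The supportable statement is that the two kinds of symptom cannot be told apart.

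A reader might also infer that chance imbalance in prior symptoms would create a false scrub effect. Under the same assumptions, the chance that at least one of the three scrubs differs from povidone-iodine by 3 or more women on prior symptoms alone is 27%, 52% and 62%. But a gap of 3 in 15 is ordinary sampling variation: 3 v 0 gives Fisher p = 0.22, and 6 v 3 gives p = 0.43. Randomization balances prior symptoms in expectation, and Step 4 shows no excess of false positives.

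Further points on the other side are fair:
- The power figures concern a test the SAP does not plan. The absence of any irritation analysis is a separate gap.
- An effect of 5% v 40% is generous. The Background cites little or no irritation for two of the scrubs, and the Methods already concede that the study may be too small.
- The infection exclusion gives examples, not a closed list, and may keep out some symptomatic women. Prior symptoms may also not all persist to follow-up.
- Surgery itself can cause symptoms that a baseline question would not remove.

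These limit the size of the problem and rule out a claim of bias towards any scrub. They do not supply the missing answer. If the only irritation output is a descriptive table by arm, that table still mixes old and new symptoms.

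**Conclusion.** The point holds as a loss of information on a secondary part of the aim. Following the plan as written, the trial can report how many women in each arm had itching, burning, irritation or treatment for vaginal infection after surgery, but not how many had them for the first time.

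The effect is to inflate each arm's rate and to dilute the difference between arms by the share with prior, persisting symptoms. At an assumed 10% to 30% with 5% v 40% new irritation, the absence of a baseline answer costs about 13 to 16 percentage points of power against counting new symptoms in all 15 women, and about 20 to 23 against restricting to symptom-free women. These sizes rest wholly on assumed rates and on a test that is not planned. The gap itself does not depend on them. With small true differences, 15 per arm is uninformative with or without the question.

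**What to change.** Ask the same itching and burning questions, plus current treatment for vaginal infection, once before the scrub, either at consent or on the day of surgery. Add the answers to the listed data items and to the SAP's baseline comparison. At 2 days, 2 weeks and 1 month, report by arm the number with new or worsened symptoms and newly started treatment relative to that answer, with the all-symptom and all-treatment figures alongside.

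The cost is two or three questions, about a minute per patient, and one table definition, with no extra visit. The report should say that symptoms caused by the surgery itself remain unseparated.

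### Use of a research ID is said to avoid bias, but nothing in the plan keeps the patient, the swab taker or the follow-up scorer from knowing the scrub

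*Combined protocol and SAP*

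**What the plan says.** The only statement on bias control is in the closing paragraphs of the Methods, just before the SAP. The text there deals with record data, for which "precautions will be taken to avoid loss of patient identifiers". It goes on: "All research investigators will only utilize the patients assigned research ID". The conclusion drawn is: "This will both protect the patient and avoid bias".

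Other provisions that bear on the point:

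- **Allocation (Methods).** Randomization is in blocks. Consenting patients receive an ID and "will be randomly assigned to one of the four arms". The text does not say when the assignment is made or opened, or who holds the list linking ID to scrub.
- **Swabs (Methods).** Three manual 10-second swabs are taken, "making sure to span the surface area of the vaginal canal with avoidance of the cervix". The person taking them is not specified.
- **Tube labels (Methods).** For the first tube: "The swab will then be broken off into a tube labeled with the patient ID, date, and “pre-scrub". For the second: "This swab will be broken off in a tube labeled with the patient ID, date, and “post-scrub". The third is labelled in the same way. No label carries the arm.
- **Follow-up (Summary and Methods).** Itching, burning and treatment for vaginal infection are reported by the patient at 2 days, 2 weeks and 1 month. Irritation and infection are also graded, by telephone or at the clinic: "The scale is a Zero to Five score, with Zero being no irritation or infection and Five being severe irritation or infection". The scorer is not specified.
- **Analysis (SAP).** Colony counts are split at 5000 per mL. Each of three scrubs is compared with povidone-iodine by Fisher's exact test at the post-scrub and post-procedure swabs. The pre-scrub result enters only the baseline comparison. No test of the 0-5 score is planned.

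**The concern.** The plan claims freedom from bias on the strength of a confidentiality measure. An investigator can use nothing but an ID and still know which scrub that ID received, because the ID conceals the person and not the treatment.

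This matters most for follow-up. Whether a patient reports burning, and whether a caller or clinic grader records a 1 or a 2, are matters of judgement that knowledge of the scrub can influence. The Specific Aims name irritation and post-surgical infection among the data to be collected, so these outcomes are not peripheral. The swabs are less exposed because the count is read in the laboratory, but how thoroughly the canal is sampled still depends on the operator.

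A reader of the finished trial who relied on the sentence would believe the scrub comparisons had a protection that they lack. Bias of this kind cannot be removed once the data are collected.

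**Working it through.** The plan gives no figure on masking, so there is none to reproduce. The check is a comparison of what the ID conceals with where judgement enters each measurement.

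**Step 1. What the stated measure covers.**

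| Person | Does the plan keep the scrub from them? | Measurement affected |
|---|---|---|
| Laboratory staff | In effect yes, if they see only the tube label (ID, date, time point); never stated | Colony counts |
| Data handler or analyst | Only if the ID-to-scrub key is withheld; not described | Coding and analysis |
| Patient | No provision | Itching, burning, reported treatment, input to the 0-5 score |
| Follow-up caller or clinic grader | No provision | 0-5 score |
| Swab taker, post-scrub and post-procedure | No provision; the assigned scrub has already been applied | The two analysed swabs |
| Swab taker, pre-scrub | No provision; time of opening the assignment not stated | Baseline comparison only |

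**Step 2. Is masking provided anywhere else?** The Summary, Background, Aims, Significance, Methods and SAP contain no mention of blinding, masking, an independent assessor, concealment of the allocation or custody of the key. The research ID is the only measure offered.

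**Step 3. Which outcomes are exposed, and how far.** The patient-reported items and the 0-5 score depend directly on the judgement of people whom the plan leaves unmasked. The colony result passes through a laboratory reading and a fixed cut-off, so its exposure is confined to swab technique.

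**Step 4. Purely illustrative arithmetic for the swabs.** The SAP gives no alpha, sidedness or positivity rates. Assume a two-sided Fisher test at 0.05, 15 v 15 (15 per arm is the plan's target), the same true positivity p in both arms, and swabbing in one arm that misses a fraction m of the positives. Then

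P(reject) = Σ over a, b of Bin(a; 15, p) × Bin(b; 15, p(1 − m)), summed where the Fisher p-value for a/15 v b/15 is at most 0.05.

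| p (assumed) | m = 0 | m = 0.2 | m = 0.3 |
|---|---|---|---|
| 0.3 | 0.017 | 0.025 | 0.035 |
| 0.5 | 0.017 | 0.033 | 0.057 |
| 0.7 | 0.017 | 0.052 | 0.106 |
| 0.9 | 0.005 | 0.122 | 0.267 |

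Differential sampling could therefore create false differences. The effect runs from negligible to large, depending on two quantities (p and m) that the documents do not give. The table shows a mechanism and predicts nothing.

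**The case against.** The strongest reply is that the outcome actually tested is well protected. The swab has a fixed duration and a described coverage, all three swabs follow one procedure, application of the scrub is standardized, and the result is a laboratory count cut at a set threshold. This stands in part. It is why the swabs are the lesser concern, but it does nothing for the follow-up outcomes.

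Several stronger readings are tempting, and the documents do not support them.

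- *The bias has a known direction, against chlorhexidine and in favour of baby shampoo.* The Background mentions a labelling controversy over chlorhexidine but then cites studies finding little or no irritation, and it describes baby shampoo as non-irritating. The ranking stated in the Summary concerns colony counts, not irritation.
- *The false-positive rate for irritation can be calculated.* The SAP plans no comparison of the 0-5 score, and the documents give neither its spread nor any likely shift. Any such figure would describe a test that the reader had added.
- *The arm is known at baseline because it is assigned at consent.* The Methods say that consenting patients are assigned but give no time. Even if the arm were known then, the pre-scrub swab enters only the baseline comparison, so it cannot move the planned efficacy tests.
- *Patients and staff will know the scrub.* The plan does not say so; it only fails to prevent it. The consent form is not among the documents reviewed and may bear on what patients are told.
- *The ID masks only the laboratory.* It could also mask an analyst if the key were withheld, although that is not described.

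**Conclusion.** The point holds as a mismatch between a claim and the measure offered for it. The research ID protects confidentiality and hides the arm at most from the laboratory and from handlers who see only the ID. The patient-reported and graded follow-up outcomes are open to bias, and the manual swabs less so.

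No size or direction can be attached from the documents. The table in the working rests entirely on assumed positivity, miss rates and alpha. The conclusion itself rests on the absence of any masking provision in the protocol and SAP, and would soften if one exists in a manual or consent form not reviewed here. The change is worth making because it is cheap, acts on outcomes named in the Aims, and can only be made before follow-up data are collected.

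**What to change.** Four changes, using existing staff:

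1. Hold the ID-to-scrub key apart from the follow-up list. Have the 2-day, 2-week and 1-month contacts made and scored by an existing team member without access to the key. Where follow-up happens at a clinic visit, score it without the scrub shown where feasible.
2. Do not tell the patient which scrub was used until after the 1-month contact, unless her care requires it.
3. As a minor addition, open the assignment only after the pre-scrub swab has been taken. This protects the baseline comparison but not the two analysed swabs.
4. Replace the claim about bias with a statement that the laboratory, the patient and the follow-up scorer are masked, and that the operating team, including whoever takes the post-scrub and post-procedure swabs, is not.

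No patients, visits or laboratory tests are added. The costs are that the scorer must be someone other than the operating clinician, which may be awkward at clinic appointments, and that the assignment must stay sealed until the operating room. The documents give no staffing, so the team should confirm that it can cover the contacts. The swab taker's knowledge of the arm at the two analysed swabs is not removed; step 4 discloses it.
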